10.3 Appendix 3: Clinical laboratory tests

10.3.1 Clinically notable laboratory values and vital signs

The complete NCI CTCAE (version 5.0) can be found at the following site:

[https://ctep.cancer.gov/protocolDevelopment/electronic_applications/docs/CTCAE_v5_Quick_Reference_8.]

10.4 Appendix 4: Participant Engagement

Not Applicable

10.5 Appendix 5: Liver safety monitoring

Not Applicable

10.5.1 Liver event and laboratory trigger definitions & follow-up requirements

Not Applicable

10.6 Appendix 6: Renal safety monitoring

Not Applicable

02-Sep-2024	Prior to DBL	Creation of amendment 1	
1. Updated the list of abbreviations.
 
2. Added R to analysis software.
 
3. Specification added on data included in the analysis, i.e. the items to which the way of reporting as 'ongoing' applies, as well as imaging data included in summaries when a participant has multiple assessments.
 
4. Addition of subgroup of interest (NET grading and primary site of cancer)
 
5. Based on eCRF update, clarification added regarding Diagnosis of Disease, NET grading, and the definition of subgroups by NEN classification.
 
6. Specification added regarding how to show rescreened participants in the summary for patient disposition.
 
7. Added listing of participants included in each analysis set.
 
8. Limited NET grading to GEP-NET.
 
Accordingly, Table 2-1 updated to define NET grading.
 
9. Added time since most recent diagnosis or relapse/progression to the summary of diagnosis and extent of cancer.
 
10. Clarification added on the population for which summary of time since initial diagnosis and time since most recent relapse/progression will be created.
 
11. Specification added on data included in concomitant medications, non-drug therapies and procedures.
 
12. The population for which the listing for central imaging assessment will be provided set as the FAS.
 
13. Clarification added on how to determine an imaging as readable but not optimal in the supplementary analysis.
 
14. Added summary of transition of intended treatment plan in the analysis of impact on treatment decision.
 
15. Weight deleted from summary of notable vital sign values since it is collected only at Day 1 post injection.
 
16. Specification added on the population for which blood concentration data will be listed, i.e. confining to participants with PK concentration in the FAS.
	List of abbreviations Sections 2.1, 2.2, 2.3.1, 2.3.2, 2.4.2, 2.5, 2.6.2, 2.7.4.2, 2.8, 4, 5.1.2.1, 5.5, 5.6, and Section 5.7

Date	Time point	Reason for update	Outcome for update	Section and title impacted (Current)
			17. Updated the imputation rules for missing dates of initial diagnosis and most recent relapse/progression. Added specification for cases where the imputed date is later than the date of informed consent. 18. Addition of Sections 5.5, 5.6 and 5.7. 19. Grammatical or editorial corrections.	

Table of contents

Table of contents	4
List of tables	5
List of figures	6

Table 5-1	Imputation of start dates (AE, CM) and assessments (LB, EG, VS)	31
Table 5-2	Imputation of end dates (AE, CM).....	31
Table 5-3	Classification of NEN	34

List of figures

Figure 1-1	Study design	9
------------	--------------------	---

List of abbreviations

AE	Adverse Event
AESI	Adverse Events of Special Interest
ATC	Anatomical Therapeutic Chemical
BMI	Body Mass Index
BP	Blood Pressure
CI	Confidence Interval
CIM	Conventional Imaging
CM	Concomitant Medications
CSR	Clinical Study Report
CT	Computerized Tomography
CTC	Common Terminology Criteria
CTCAE	Common Terminology Criteria for Adverse Events
CV	Coefficient of Variation
ECG	Electrocardiogram
ECOG	Eastern Cooperative Oncology Group
EFF	Efficacy Analysis Set
EG	Electrocardiogram results
FAS	Full Analysis Set
FN	False Negative
FP	False Positive
FU	Follow-Up
HV	Healthy Volunteer
LB	Laboratory test results
LLOQ	Lower Limit of Quantification
MBq	Mega-Becquerel
MedDRA	Medical Dictionary for Regulatory Activities
MiNEN	Mixed Neuroendocrine-non-neuroendocrine Neoplasm
MRI	Magnetic Resonance Imaging
NCI	National Cancer Institute
NEC	Neuroendocrine Carcinoma
NEN	Neuroendocrine Neoplasm
NET	Neuroendocrine Tumor
NPV	Negative Predictive Value
PAS	Pharmacokinetic Analysis Set
PD	Pharmacodynamic(s)
PET	Positron Emission Tomography
PK	Pharmacokinetic(s)
PPV	Positive Predictive Value
PT	Preferred Term
RAP	Reporting & Analysis Process
SAE	Serious Adverse Event
SAP	Statistical Analysis Plan
SAS	Statistical Analysis System
SD	Standard Deviation
SOC	System Organ Class

SPECT	Single-photon Emission Computerized Tomography
SSTR	Somatostatin Receptor
TEAE	Treatment Emergent Adverse Event
TN	True Negative
TP	True Positive
VS	Vital Signs
WBC	White blood cells
WHO	World Health Organization
WHO-DD	World Health Organization Drug Dictionary

1 Introduction

This statistical analysis plan (SAP) describes all planned analyses for the Clinical Study Report (CSR) of study CAAA501A11301, a prospective, open-label, phase III study of [⁶⁸Ga]Ga-DOTA-TATE in patients with neuroendocrine neoplasms (NENs) and healthy volunteers in Japan.

[figure not shown]
The content of this SAP is based on protocol CAAA501A11301 version 01. All decisions regarding final analysis, as defined in the SAP document, have been made prior to database lock of the study data.

1.1 Study design

This prospective, open-label, multi-center, single arm, phase III study, will enroll approximately 47 adult male or female participants with NENs and 23 HVs. Of all the participants with NENs, the number of participants with suspected NENs is limited to up to 5 with negative conventional imaging (CIM) result by central read in order to enroll sufficient number of participants with positive result in CIM. Negative CIM result by central read is applicable for patients who do not show any lesions based on CIM by central read. All eligible participants will undergo [⁶⁸Ga]Ga-DOTA-TATE PET/CT imaging. [⁶⁸Ga]Ga-DOTA-TATE will be administered intravenously at a single dose of 2 MBq/kg (0.054 mCi/kg) of body weight up to a maximum total dose of 200 MBq (5.4 mCi), and imaging will be acquired 40 to 90 minutes after the intravenous injection of [⁶⁸Ga]Ga-DOTA-TATE.

The purpose of this study is to evaluate the diagnostic performance of [⁶⁸Ga]Ga-DOTA-TATE PET/CT imaging compared with the CIM as standard of truth in patients with NENs and HVs. The data from this study will provide the evidence for diagnosis use of [⁶⁸Ga]Ga-DOTA-TATE PET/CT imaging in patient with NENs in Japan.

Figure 1-1 Study design

NENs: Neuroendocrine neoplasms, CT: Computed Tomography, MRI: Magnetic Resonance Imaging, CIM: Conventional Imaging, PET: Positron Emission Tomography

1.2 Study objectives, endpoints and estimands

Endpoints will be evaluated based on central read unless otherwise specified.

Table 1-1 Objectives and related endpoints

Objective(s)	Endpoint(s)
Primary objective(s)	Endpoint(s) for primary objective(s)

 To evaluate the subject-level sensitivity of [⁶⁸Ga]Ga-DOTA-TATE PET/CT imaging for NENs. To evaluate the subject-level specificity of [⁶⁸Ga]Ga-DOTA-TATE PET/CT imaging for NENs. 	
 Proportion of [⁶⁸Ga]Ga-DOTA-TATE positive participants (TP participants) among CIM positive participants (TP or FN participants). Proportion of [⁶⁸Ga]Ga-DOTA-TATE negative participants (TN participants) among CIM negative participants (TN or FP participants).
Secondary objective(s)	Endpoint(s) for secondary objective(s)

 To evaluate subject-level positive predictive values (PPV) of [⁶⁸Ga]Ga-DOTA-TATE PET/CT imaging. To evaluate subject-level negative predictive values (NPV) of [⁶⁸Ga]Ga-DOTA-TATE PET/CT imaging. To evaluate subject-level accuracy of [⁶⁸Ga]Ga-DOTA-TATE PET/CT imaging. To evaluate region-level sensitivity of [⁶⁸Ga]Ga-DOTA-TATE PET/CT imaging for NENs. To evaluate region-level specificity of [⁶⁸Ga]Ga-DOTA-TATE PET/CT imaging for NENs. To evaluate region-level positive predictive values (PPV) of [⁶⁸Ga]Ga-DOTA-TATE PET/CT imaging. To evaluate region-level negative predictive values (NPV) of [⁶⁸Ga]Ga-DOTA-TATE PET/CT imaging. To evaluate region-level accuracy of [⁶⁸Ga]Ga-DOTA-TATE PET/CT imaging. To evaluate number of lesions detected by [⁶⁸Ga]Ga-DOTA-TATE PET/CT imaging and each CIM at region-level. To evaluate the impact of [⁶⁸Ga]Ga-DOTA-TATE PET/CT imaging on treatment decision. 	
 Proportion of participants who are positive on both [⁶⁸Ga]Ga-DOTA-TATE PET/CT imaging and CIM (TP participants) among participants who are positive on [⁶⁸Ga]Ga-DOTA-TATE PET/CT imaging (TP or FP participants). Proportion of participants who are negative on both [⁶⁸Ga]Ga-DOTA-TATE PET/CT imaging and CIM (TN participants) among participants who are negative on [⁶⁸Ga]Ga-DOTA-TATE PET/CT imaging (TN or FN participants). Proportion of participants who have consistent results (i.e. TP or TN participants) among all participants assessed by [⁶⁸Ga]Ga-DOTA-TATE PET/CT imaging and CIM. Proportion of [⁶⁸Ga]Ga-DOTA-TATE positive regions (TP regions) among CIM positive regions (TP or FN regions). Proportion of [⁶⁸Ga]Ga-DOTA-TATE negative regions (TN regions) among CIM negative regions (TN or FP regions). Proportion of regions which are positive on both [⁶⁸Ga]Ga-DOTA-TATE PET/CT imaging and CIM (TP regions) among regions which are positive on [⁶⁸Ga]Ga-DOTA-TATE PET/CT imaging (TP or FP regions). Proportion of regions who are negative on both [⁶⁸Ga]Ga-DOTA-TATE PET/CT imaging and CIM (TN regions) among regions which are negative on [⁶⁸Ga]Ga-DOTA-TATE PET/CT imaging (TN or FN regions). Proportion of regions which have consistent results (i.e. TP or TN regions) among all regions assessed by [⁶⁸Ga]Ga-DOTA-TATE PET/CT imaging and CIM. Number of lesions detected by [⁶⁸Ga]Ga-DOTA-TATE PET/CT imaging and each CIM at region-level. Percentage of patients who underwent a change in intended treatment plan attributed to the [⁶⁸Ga]Ga-DOTA-TATE PET/CT imaging as assessed by pre and post imaging questionnaires.

Objective(s)	Endpoint(s)

• To evaluate inter-reader variability.• To evaluate safety and tolerability of [68Ga]Ga-DOTA-TATE.• To evaluate PK of [68Ga]Ga-DOTA-TATE.• To evaluate lesion-level concordance for SSTR between [68Ga]Ga-DOTA-TATE PET/CT imaging local read and local histopathology results.	
• Inter-reader agreement on [68Ga]Ga-DOTA-TATE PET/CT imaging.• Incidence of Treatment emergent adverse event (TEAE) within 8 days after [68Ga]Ga-DOTA-TATE administration.• Pharmacokinetic parameters (AUCinf, AUClast, Cmax, Tmax, T1/2, CL, Vz etc.).• Lesion-level concordance rate for SSTR between [68Ga]Ga-DOTA-TATE PET/CT imaging local read and local histopathology result among lesions that local histopathology result are available.

1.2.1 Primary estimand(s)

The primary clinical question of interest is: What is the probability that [⁶⁸Ga]Ga-DOTA-TATE PET/CT imaging truly detects tumor lesion(s) in subject-level for NENs using CIM (including [¹¹¹In]In-Pentetreotide SPECT/CT and High Resolution CT with contrast (or MRI if CT with contrast is medically contraindicated) as standard of truth).

The justification for the primary estimand is that it will capture the diagnostic performance of [⁶⁸Ga]Ga-DOTA-TATE PET/CT imaging in detecting tumor lesion(s) in NENs subjects. For this reason, participants with confirmed or suspected NENs will be investigated with CIM obtained on or before screening phase (HVs will be categorized as CIM negative without performing CIM) and confirmed or suspected NENs and HVs will be investigated with [⁶⁸Ga]Ga-DOTA-TATE PET/CT imaging on treatment phase, and the results of [⁶⁸Ga]Ga-DOTA-TATE PET/CT imaging will be compared against the results of CIM as standard of truth. The primary estimands are described by the following attributes:

Primary estimand 1:

1. Population: Patients who show at least one lesion based on CIM by central read, received [⁶⁸Ga]Ga-DOTA-TATE, completed a PET/CT scan and had a central read of the [⁶⁸Ga]Ga-DOTA-TATE PET/CT imaging.
2. Variable: The result of [⁶⁸Ga]Ga-DOTA-TATE PET/CT imaging (positive (i.e., showing at least one lesion) or negative (i.e., not showing any lesion)). In the population above, a participant with positive on [⁶⁸Ga]Ga-DOTA-TATE PET/CT imaging corresponds to True positive (TP) and a participant with negative on [⁶⁸Ga]Ga-DOTA-TATE PET/CT imaging corresponds to False negative (FN).
3. Treatment of interest: [⁶⁸Ga]Ga-DOTA-TATE injected as a single intravenous dose of 2 MBq/kg (0.054 mCi/kg) of body weight up to a maximum total dose of 200 MBq (5.4 mCi).
4. Intercurrent events: None
5. Summary measure: Estimate of proportion of participants who test positive on [⁶⁸Ga]Ga-DOTA-TATE PET/CT imaging (TP) among those who are CIM positive (TP+FN according to [⁶⁸Ga]Ga-DOTA-TATE PET/CT imaging) (subject-level sensitivity), along with 95% confidence interval.

Primary estimand 2:

1. Population: Participants who do not show any lesions based on CIM by central read or are HVs, received [⁶⁸Ga]Ga-DOTA-TATE, completed a PET/CT imaging and had a central read of the [⁶⁸Ga]Ga-DOTA-TATE PET/CT imaging. The population selection depends on the results of central read, therefore patients with NENs can be included if applicable, in addition to HVs who will be categorized as CIM negative without performing CIM.
2. Variables: The result of [⁶⁸Ga]Ga-DOTA-TATE PET/CT imaging (positive or negative). In the population above, a participant who test positive on [⁶⁸Ga]Ga-DOTA-TATE PET/CT imaging corresponds to False positive (FP) and a participant who test negative on [⁶⁸Ga]Ga-DOTA-TATE PET/CT imaging corresponds to True negative (TN).
3. Treatment of interest: [⁶⁸Ga]Ga-DOTA-TATE injected as a single intravenous dose of 2 MBq/kg (0.054 mCi/kg) of body weight up to a maximum total dose of 200 MBq (5.4 mCi).
4. Intercurrent events: None.
5. Summary measure: Estimate of proportion of participants who test negative on [⁶⁸Ga]Ga-DOTA-TATE PET/CT imaging (TN) among those who are CIM negative (TN+FP according to [⁶⁸Ga]Ga-DOTA-TATE PET/CT imaging) (subject-level specificity), along with 95% confidence interval.

2 Statistical methods

2.1 Data analysis general information

The final analysis will be performed by Novartis. SAS version 9.4 or later and R version 4.3.1 or later will be used to perform all data analyses and to generate tables, figures and listings.

Data included in the analysis

Only one final analysis is planned for the co-primary endpoints. All statistical analyses will be performed using all data collected in the database up to the database lock date. The database lock date for the final analysis of study data will be established after all enrolled participants have completed End of study visit (Last Patient Last Visit).

All events with start date before or on the database lock date and not having documented end date will be reported as 'ongoing'. This approach applies, in particular, to adverse events, prior anti-neoplastic medication/ anti-neoplastic radiotherapies, and concomitant medication/ non-drug therapies/ non-drug procedures reports. For these cases, the end date will not be imputed and therefore will not appear in the listings.

For participants who have both High Resolution CT with contrast and MRI imaging as CIM, the results of MRI will be used for summaries. For participants who have multiple imaging assessments of the same modality on different imaging dates, the results on the latest assessment date will be used for summaries.

Participant categorization

For some efficacy analyses (subject/region-level sensitivity, specificity, PPV, NPV and accuracy), HVs will be categorized as CIM negative population (TN or FP) without CIM. If there are participants enrolled as patients with suspected NENs but founded not to have NENs based on CIM, they will be also categorized in this population.

Other than those above:

Analyses will be conducted by patients with confirmed/suspected NENs and HVs. Results will be presented by population unless otherwise specified.

General analysis conventions

Qualitative data (e.g., gender, race, etc.) will be summarized by frequencies and percentages; a missing category will be included as applicable. Percentages will be calculated using the number of participants in the relevant population or subgroup as the denominator.

Quantitative data (e.g., age, body weight, etc.) will be summarized by appropriate descriptive statistics (i.e. N, mean, standard deviation, median, 25th percentile, 75th percentile, minimum, and maximum).

2.1.1 General definitions

Study treatment/ drug

Study treatment/ drug is [⁶⁸Ga]Ga-DOTA-TATE administered intravenously at a dose of 2 MBq/kg (0.054 mCi/kg) of body weight up to a total maximum dose of 200 MBq (5.4 mCi) even if no [⁶⁸Ga]Ga-DOTA-TATE PET/CT scan was acquired.

Study day

The study day describes the day of the event or assessment date, relative to the reference start date.

The study day is defined as:

- The date of the event (visit date, onset date of an event, assessment date etc.) – reference start date + 1 if event is on or after the reference start date;
- The date of the event (visit date, onset date of an event, assessment date etc.) – reference start date if event precedes the reference start date.

The reference date for all assessments is the start of study treatment.

The study day will be displayed in the data listings. If an event starts before the reference start date, the study day displayed on the listing will be negative.

Time unit

A year length is defined as 365.25 days. A month length is 30.4375 days (365.25/12). If duration is reported in months, duration in days will be divided by 30.4375. If duration is reported in years, duration in days will be divided by 365.25.

Baseline

The last available assessment including unscheduled assessments before injection of study drug is taken as “baseline” value or “baseline” assessment.

If participants have no value as defined above, the baseline result will be missing.

On-treatment assessment/event and observation periods

The overall observation period will be divided into three mutually exclusive segments:

1. Pre-treatment period: from day of participant’s informed consent to the day before dosing of investigational drug.
2. On-treatment period: from day of dosing of investigational drug to 8 days after dosing of investigational drug. (i.e. Day 1 – Day 9)
3. Post-treatment period: starting 9 days after dosing of investigational drug. (i.e. start from Day 10)

If dates are incomplete in a way that clear assignment to pre-, on-, post-treatment period cannot be made, then the respective data will be assigned to the on-treatment period.

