8.4.4 Clinical safety laboratory tests

Local laboratory will be used for analysis of hematology, chemistry, urinalysis, coagulation, and pregnancy testing (if applicable) according to the schedule of assessments as described in [Table 1-2](#). The samples need to be taken prior to the injection of the [⁶⁸Ga]Ga-DOTA-TATE.

Urine samples will be collected at screening, at imaging day and safety follow-up by dipstick and analyzed locally at the clinical site if dipstick results are abnormal.

All abnormal lab results must be evaluated for criteria defining an adverse event and reported as such if the criteria are met. For those lab adverse events, repeated evaluations are mandatory until normalization of the result(s) or until the result is no longer considered to be clinically significant.

Abnormal laboratory values or test results constitute adverse events only if they fulfill at least one of the following criteria: 1) they induce clinical signs or symptoms, 2) they are considered clinically significant, or 3) they require concomitant therapy or procedures. Clinically significant abnormal laboratory values or test results should be identified through a review of values outside of normal ranges/clinically notable ranges, significant changes from screening or the previous visit.

At any time during the study, abnormal laboratory parameters which are clinically relevant, whether specifically requested in the protocol or not, will be recorded on the AE eCRF page. Laboratory data will be summarized using the Common Terminology Criteria for Adverse Events (CTCAE) version 5.0 ([Section 10.3.1](#)). Additional analyses are left to the discretion of the Investigator.

Novartis must be provided with a copy of the local laboratory's certification (if applicable), and a tabulation of the normal ranges and units of each parameter collected in the eCRF. Any changes regarding normal ranges and units for laboratory values assessed during the study must be reported via an updated tabulation indicating the date of revalidation.

The Investigator is responsible for reviewing all laboratory reports for participants in the study and evaluating any abnormalities for clinical significance.

Table 8-4 Laboratory assessments

Test Category	Test Name

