9.4.2 Safety endpoints

For all safety analyses, the safety set will be used. All listings and tables will be presented by group (i.e. Patients with confirmed/suspected NENs and HVs).

Safety summaries (tables, figures) include only data from the on-treatment period with the exception of baseline data which will also be summarized where appropriate (e.g. change from baseline summaries). In addition, a separate summary for death including on treatment and post treatment deaths will be provided. In particular, summary tables for adverse events (AEs) will summarize only on-treatment events, with a start date during the on-treatment period (treatment-emergent AEs).

The overall observation period will be divided into three mutually exclusive segments:

1. Pre-treatment period: from day of participant's informed consent to the day before dosing of investigational drug.
2. On-treatment period: from day of dosing of investigational drug to 8 days after dosing of investigational drug.
3. Post-treatment period: starting 9 days after dosing of investigational drug.

Adverse events

The incidence of treatment-emergent adverse events (new or worsening from baseline) will be summarized by system organ class and or preferred term, severity (based on CTCAE grades), type of adverse event, relation to study treatment.

Serious adverse events, non-serious adverse events and adverse events of special interest (AESI) during the on-treatment period will be tabulated.

All deaths (on-treatment and post-treatment) will be summarized.

All AEs, deaths, and serious adverse events (including those from the pre and post-treatment periods) will be listed and those collected during the pre-treatment and post-treatment period will be flagged.

Vital signs

Notable vital sign values will be summarized by visit/time.

12-lead ECG

ECG abnormalities will be summarized.

Clinical laboratory evaluations

Grading of laboratory values will be assigned programmatically as per NCI Common Terminology Criteria for Adverse Events (CTCAE) version 5.0. The calculation of CTCAE grades will be based on the observed laboratory values only, clinical assessments will not be taken into account.

CTCAE Grade 0 will be assigned for all non-missing values not graded as 1 or higher. Grade 5 will not be used.

For laboratory tests where grades are not defined by CTCAE version 5.0, results will be categorized as low/normal/high based on laboratory normal ranges.

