2.7.3 Laboratory data

Grading of laboratory values will be assigned programmatically as per NCI CTCAE version 5.0. The calculation of CTCAE grades will be based on the observed laboratory values only, clinical assessments will not be taken into account.

CTCAE Grade 0 will be assigned for all non-missing values not graded as 1 or higher. Grade 5 will not be used.

For laboratory tests where grades are not defined by CTCAE version 5.0, results will be categorized as low/normal/high based on laboratory normal ranges.

The following summaries will be generated separately for hematology, and biochemistry tests:

For laboratory tests where grades are defined by CTCAE version 5.0:

- Worst post-baseline CTCAE grade (regardless of the baseline status). Each participant will be counted only once for the worst grade observed post-baseline.
- Shift tables using CTCAE version 5.0 grades to compare baseline to the worst on-treatment value.

For laboratory tests where grades are not defined by CTCAE version 5.0:

- Shift tables using the low/normal/high/ (low and high) classification to compare baseline to the worst on-treatment value.

Listing of laboratory data will be produced with values flagged to show the corresponding CTCAE version 5.0 grades if applicable and the classifications relative to the laboratory normal ranges.

All urinalysis and coagulation data will be listed.

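### As written, the pre-injection Day 1 laboratory sample is both the baseline and an on-treatment value, so the hematology and biochemistry shift tables cannot show improvement and disagree with the neighbouring worst-grade table

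*SAP*

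**What the plan says.** SAP 2.1.1 states that "The overall observation period will be divided into three mutually exclusive segments". The first runs from "informed consent to the day before dosing of investigational drug". The second is given as "On-treatment period: from day of dosing of investigational drug to 8 days after dosing of investigational drug", which the SAP glosses as Day 1 to Day 9. Protocol 9.4.2 has the same day-based periods.

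Baseline follows a different clock. In SAP 2.1.1, "The last available assessment including unscheduled assessments before injection of study drug is taken as" the baseline value.

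Protocol Table 1-2 schedules hematology and chemistry at Screening, on Day 1 in the pre-injection column, and at the Day 8 visit. No laboratory sample is scheduled on Day 1 after the injection. Protocol 8.4.4 agrees: "The samples need to be taken prior to the injection of the" study agent.

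SAP 2.7.3 plans two summaries for CTCAE-graded tests, side by side: "Worst post-baseline CTCAE grade (regardless of the baseline status" and "Shift tables using CTCAE version 5.0 grades to compare baseline to the worst on-treatment value". Tests without CTCAE grades get a low/normal/high shift table, with a combined low-and-high category, also against the worst on-treatment value. Protocol 9.4.2 has the same summaries.

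**The concern.** Two clocks are in use on Day 1, and neither document has a rule to reconcile them. Pre-treatment ends the day before dosing and the periods do not overlap, so nothing collected on Day 1 can be pre-treatment. The pre-injection sample is therefore on-treatment by date and baseline by its relation to the injection.

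A shift table is meant to set what was measured before the drug against what was measured after it. If the pre-drug value also sits on the after side, the table cannot show a return towards normal. It also shows an unchanged result for someone with no post-injection sample at all. The table beside it uses post-baseline values, so two tables in one section would describe the same person from different data.

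The day-based rule also reaches adverse events. One with onset on Day 1 before the injection has a start date in the on-treatment period and is summarized as treatment-emergent, although the endpoint in Protocol Table 3-1 and SAP Table 1-1 concerns events after administration.

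**Working it through.** **1. Reproduce the period limits.** SAP 2.1.1 sets study day = date − dosing date + 1 on or after dosing, and date − dosing date before it.
- Day of dosing: 0 + 1 = Day 1.
- 8 days after: 8 + 1 = Day 9.
- 9 days after: 9 + 1 = Day 10.
- Day before: Day −1.

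This matches the SAP's Day 1 to Day 9, with post-treatment from Day 10.

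**2. Place the scheduled samples.**
- Screening (Day −35 to −1): pre-treatment.
- Day 1 pre-injection: study day 1, so on-treatment. It is also the baseline whenever it was taken.
- Follow-up (Day 8 ± 1, so Day 7 to 9): on-treatment.

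**3. Derive the shift-table entry.** Let b be the baseline grade (Day 1) and f the Day 8 grade. As written, the worst on-treatment grade is max(b, f). With post-injection values only, it is f.

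Grades 0 to 4 give a 5 × 5 table (SAP 2.7.3 does not use grade 5). Improvement cells have f < b, so there are 0 + 1 + 2 + 3 + 4 = 10. Since max(b, f) is never below b, 0 of the 10 can be filled as written; all 10 can be with post-injection values.

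**4. Examples.**

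| Baseline | Day 8 | As written | Post-injection only |
|---|---|---|---|
| Grade 2 | Grade 0 | 2 to 2 | 2 to 0 |
| Grade 1 | Grade 0 | 1 to 1 | 1 to 0 |
| Grade 0 | Grade 2 | 0 to 2 | 0 to 2 |
| Low | High | Low to low and high | Low to high |
| High | Normal | High to high | High to normal |
| Any | Missing | No shift | Missing |

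In the first two rows the worst post-baseline table shows grade 0. The third row shows that a measured worsening is unaffected.

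SAP 2.1 allows a missing category where applicable. As written it would not apply in the last row, because the Day 1 value counts as a non-missing on-treatment value.

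**5. How many entries change.** The documents give no laboratory abnormality rate, so the following is illustrative. Let p be the probability of an abnormal value at each of Day 1 and Day 8, and ρ the correlation between the two. The share abnormal at either visit is 2p − [p² + ρp(1 − p)]. The excess over Day 8 alone is p(1 − p)(1 − ρ), the share abnormal on Day 1 but normal on Day 8. With 70 participants:

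| p | ρ | Day 8 alone | Either visit | Excess |
|---|---|---|---|---|
| 5% | 0 | 3.5 | 6.8 | 3.3 |
| 5% | 0.5 | 3.5 | 5.2 | 1.7 |
| 10% | 0 | 7.0 | 13.3 | 6.3 |
| 10% | 0.5 | 7.0 | 10.2 | 3.2 |
| 20% | 0 | 14.0 | 25.2 | 11.2 |
| 20% | 0.5 | 14.0 | 19.6 | 5.6 |

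Two samples about a week apart in one person are unlikely to be independent, so the ρ = 0.5 rows are the more plausible. If 0% to 10% lack a Day 8 sample (also an assumption), 70 × 0 to 70 × 0.10 gives 0 to 7 participants shown as unchanged who should be missing.

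**6. Adverse events.** One participant whose only on-treatment event began on Day 1 before the injection would add 1/23 = 4.3 percentage points in the healthy volunteers, or 1/47 = 2.1 in the patients. The documents give no expected number of such events.

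**The case against.** The best defence is that the authors did not mean the baseline sample to count as on-treatment. SAP 2.7 limits safety summaries to on-treatment data and treats baseline data as an exception. A comparison of baseline with on-treatment values makes sense only if the two sides are different records, and the adjacent bullet says post-baseline. This is good evidence of intent. It does not stand as a rule: the SAP 2.7 wording lets baseline data be shown in addition and does not remove the Day 1 sample from Day 1 to Day 9. For vital signs and ECG the SAP names time points such as Day 1 post-injection; the shift tables have no such restriction.

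It can also be said that the harm is small, and most of this stands. A pre-dose abnormality stays in its own baseline row and does not look like a new finding. For graded tests the worst post-baseline table already gives the clean post-dose grade. Improvement is of little safety interest for a single diagnostic dose that Protocol 6.1 describes as having no therapeutic effect. Showing an unmeasured participant as unchanged is harder to excuse.

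For adverse events, counting all of Day 1 is a conservative date convention, in line with SAP 2.1.1, which assigns unclear dates to the on-treatment period. Protocol 9.4.2 also describes treatment-emergent events as new or worsening from baseline, which points away from pre-injection events. Separating them needs an onset time or a before/after flag, and the documents do not say that either is collected. This is why the adverse-event part is secondary.

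**Conclusion.** The shift-table rule is wrong as written and should be corrected. For any dosed participant with the scheduled Day 1 sample, one value sits on both sides of the comparison. If that sample is missing, screening is the baseline and there is no overlap.

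The reach is the hematology and biochemistry shift tables. Entries change only where baseline is worse than Day 8, where Day 8 is missing, or where the direction reverses. Under the assumed rates that is about 2 to 11 of 70 per test, plus 0 to 7 for missing Day 8 samples. Vital signs and ECG are summarized at named time points, and urinalysis and coagulation are only listed.

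Four stronger readings are tempting and are not supported:
- That results change for all 70 participants. The overlap can exist for all, but most displayed entries would be the same.
- That a secondary endpoint is corrupted by the laboratory rule. The named safety endpoint is the incidence of treatment-emergent adverse events; laboratory tables support the safety objective descriptively.
- That the rule conceals harm. A worsening measured on Day 8 still appears, and the co-primary endpoints and sample size are unaffected.
- That the treatment-emergent rate is inflated by a known amount. The rule would admit pre-injection Day 1 events, but nothing in the documents says whether any will occur.

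**What to change.** In SAP 2.1.1 and 2.7.3, and in Protocol 9.4.2:
- Define on-treatment assessments as those made after the injection through Day 9.
- Treat Day 1 samples labelled pre-injection as baseline or pre-treatment only.
- Base both laboratory tables on the worst post-injection value, with a missing category for participants who have none.
- Class an adverse event as pre-treatment where a recorded onset time or a before/after-injection flag shows onset before the injection on Day 1. Keep every other Day 1 event as on-treatment.

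The laboratory part costs a few sentences and a slightly more detailed Day 1 derivation. The schedule already labels the pre-injection samples, and injection time is already needed for the planned injection-to-scan interval. The adverse-event part changes results only if onset time or a flag is available. If it is not, every Day 1 event stays where the SAP now puts it, unless the eCRF is changed.
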